9.5.2.2. Statistical Analysis of Pharmacokinetic Endpoints

Plasma concentration-time data will be analyzed using noncompartmental methods and summarized with descriptive statistics.

In the primary analysis, Cmax, AUClast, and AUC_{inf} will be compared for subjects in the moderate HI group (as defined by NCI-ODWG criteria) to those of normal hepatic function. Note that when percent extrapolated AUC (%AUC_{extr}) is greater than 20%, AUC_{inf} and related parameters will be summarized with and without those individuals having >20% AUC_{extr}. These comparisons between the moderate HI group (as defined by NCI-ODWG criteria) with the healthy control group will be made using an analysis of variance model on logarithm-transformed Cmax, AUClast, and AUC_{inf}. The resulting point estimates (least-squares means) differences (HI/normal hepatic function), and 90% confidence intervals

(CIs) for the difference will be exponentiated to get the ratio and corresponding 90% CI of the ratio on the untransformed scale and will be presented for each HI cohort (normal and moderate HI as defined by NCI-ODWG criteria).

Each comparison will also be made by performing an analysis of covariance (ANCOVA) on the logarithm-transformed Cmax, AUClast, and AUCinf including the hepatic function, sex, age, and weight as factors. Within the framework of ANCOVA, the estimate and 90% CI will be provided for the ratio of central values between the HI group and normal hepatic function group.

9.6. Interim Analyses

PK and safety analyses may be conducted as ongoing basis.

10. APPENDICES - SUPPORTING DOCUMENTATION AND OPERATIONAL CONSIDERATIONS

10.1. Appendix 1 Regulatory and Ethical Considerations

10.1.1. Regulatory Compliance

The study protocol, the IB, available safety information, recruitment procedures (eg, advertisements), subject information and consent form, any subject written instructions to be given to the subject, information about payments and compensation available to the subjects, and documentation evidencing the Investigator's qualifications should be submitted to the independent IRB for ethical review and approval according to local regulations, prior to the study start. The written approval should identify all documents reviewed by name and version.

Changes in the conduct of the study or planned analysis will be documented in a protocol amendment and/or the SAP. Written approval of all protocol amendments and changes to any of the above listed documents must be obtained from the IRB.

The Investigator should notify the IRB of deviations from the protocol or SAEs occurring at the study site and other AE reports in accordance with local procedures.

The Sponsor will appoint all Investigators. Among other possible duties, each Investigator will be responsible for reviewing the Final Clinical Study Report and testifying to the accuracy of the description of the study conduct. Because the Investigators should have personal knowledge of the conduct of the study, they will normally be chosen from among those investigators who have enrolled and treated at least one subject. However, where any Investigator has special knowledge of the field or of the study, the Investigator can be chosen prior to enrollment of the first subject. In all cases, the Investigator must be chosen prior to locking the data base.

10.1.2. Compliance Statement, Ethics, and Regulatory Compliance

This study will be conducted in compliance with the protocol, the ethical principles that have their origin in the Declaration of Helsinki, the International Council for Harmonization (ICH) consolidated Guideline E6 for Good Clinical Practice (GCP) (CPMP/ICH/135/95), and applicable regulatory requirement(s) including the following:

- US Food and Drug Administration (FDA) GCP Regulations: Code of Federal Regulations Title 21, parts 11, 50, 54, 56 and 312 as appropriate and/or;
- Other applicable local regulations.

In addition, the Investigator will inform the Sponsor in writing within 24 hours of any urgent safety measures taken by the Investigator to protect the study subjects against any immediate hazard, and of any suspected/actual serious GCP non-compliance that the Investigator becomes aware of.

10.1.3. Supply of New Information Affecting the Conduct of the Study

When new information becomes available that may adversely affect the safety of subjects or the conduct of the study, the Sponsor will inform all Investigators involved in the clinical study,

IRBs, and regulatory authorities of such information, and when needed, will amend the protocol and/or subject information.

The Investigator should immediately inform the subject whenever new information becomes available that may be relevant to the subject's consent or may influence the subject's willingness to continue participation in the study. The communication should be documented on medical records, for example, and it should be confirmed whether the subject is willing to remain in the study.

If the subject information is revised, it must be re-approved by the IRB. The Investigator will obtain written informed consent to continue participation with the revised written information even if subjects were already informed of the relevant information. The Investigator or other responsible personnel who provided explanations and the subject should sign and date the revised ICF.

10.1.4. Informed Consent

In obtaining and documenting informed consent, the Investigator should comply with the applicable regulatory requirements, and should adhere to GCP and to the ethical principles that have their origin in the Declaration of Helsinki. The ICF and any revision(s) should be approved by the IRB prior to being provided to potential subjects.

The subject's written informed consent should be documented in the subject's medical records. The ICF should be signed and personally dated by the subject and by the person who conducted the informed consent discussion (not necessarily the Investigator). The original signed ICF should be retained in accordance with institutional policy, and a copy of the signed ICF should be provided to the subject. The date and time (if applicable) that informed consent was given must be recorded in the eCRF.

If the subject cannot read, then according to ICH GCP Guideline, Section 4.8.9, an impartial witness should be present during the entire informed consent discussion. This witness should sign the ICF after the subject has consented to their participation. By signing the ICF, the witness attests that the information in the ICF and any other written information was adequately explained to and apparently understood by the subject and that informed consent was freely given by the subject.

A separate special consent for inherited genetic analysis will be obtained from subjects in accordance with health authorities in their particular region/country.

Suggested model text for the ICF for the study and any applicable subparts (PK, PD, etc) is provided in the Sponsor's ICF template for the Investigator to prepare the documents to be used at his or her study site. Updates to applicable forms will be communicated via letter from the Sponsor.

For study sites in the US, an additional consent is required for the Health Insurance Portability and Accountability Act.

10.1.5. Subject Confidentiality

The Investigators and the Sponsor will preserve the confidentiality of all subjects taking part in the study, in accordance with GCP and local regulations.

The Investigator must ensure that the subject's anonymity is maintained. On the eCRFs or other documents submitted to the Sponsor, subjects should be identified by a unique subject identification (SID) as designated by the Sponsor. Documents that are not for submission to the Sponsor (eg, signed ICF) should be kept in strict confidence by the Investigator.

In compliance with ICH GCP Guidelines, it is required that the Investigator and institution permit authorized representatives of the company, of the regulatory agency(s), and the independent IRB/EC direct access to review the subject's original medical records for verification of study-related procedures and data. The Investigator is obligated to inform the subject that his/her study-related records will be reviewed by the above named representatives without violating the confidentiality of the subject.

10.1.6. Data Integrity and Quality Assurance

10.1.6.1. Monitoring and Inspections

The Sponsor monitor and regulatory authority inspectors are responsible for contacting and visiting the Investigator for the purpose of inspecting the facilities and, upon request, inspecting the various records of the study (eg, eCRFs, source data, and other pertinent documents).

The verification of adherence to the protocol; completeness, accuracy, and consistency of the data; and adherence to ICH GCP and local regulations on the conduct of clinical research will be accomplished through a combination of onsite visits by the monitor and review of study data remotely. The frequency of the monitoring visit will vary based on the activity at each study site. The monitor is responsible for inspecting the eCRFs and ensuring completeness of the study essential documents. The monitor should have access to subject medical records and other study-related records needed to verify the entries on the eCRFs. Detailed information is provided in the monitoring plan.

The monitor will communicate deviations from the protocol, SOPs, GCP and applicable regulations to the Investigator and will ensure that appropriate action (s) designed to prevent recurrence of the detected deviations is taken and documented.

The Investigator agrees to cooperate with the monitor to ensure that any problems detected in the course of these monitoring visits are addressed to the satisfaction of the Sponsor and documented.

In accordance with ICH GCP and the Sponsor's audit plans, this study may be selected for audit by representatives from the Sponsor. Audit of study site facilities (eg, pharmacy, drug storage areas, laboratories) and review of study related records will occur in order to evaluate the study conduct and compliance with the protocol, ICH GCP, and applicable regulatory requirements. The Investigator should respond to audit findings.

In the event that a regulatory authority informs the Investigator that it intends to conduct an inspection, the Sponsor shall be notified immediately.

10.1.6.2. Data Collection

An eCRF must be completed for each subject. Screen failure information will be collected at the clinical site in a log. All data collected during the study will be recorded in the individual,

subject-specific eCRF. Instructions will be provided for the completion of the eCRF and any corrections made will be automatically documented via an “audit trail.”

The eCRF should be kept current to enable the study monitor to review the subject’s status throughout the course of the study. Upon completion of the subject’s eCRF, it will be reviewed and signed off by the Investigator via the electronic data capture (EDC) system’s electronic signature. This signature will indicate that the Investigator inspected or reviewed the data in the subject-specific eCRF, the data queries, and the site notifications and agrees with the eCRF content.

10.1.6.3. Data Management

Each subject will be identified in the database by a unique SID.

To ensure the quality of clinical data across all subjects and study sites, a contract research organization (CRO) Clinical and Data Management review will be performed on subject data according to specifications developed by the Sponsor. Data will be vetted both electronically by programmed data rules within the application and manually. Queries generated by rules and raised by reviewers will be generated within the EDC application. During this review, subject data will be checked for consistency, completeness and any apparent discrepancies.

Data received from external sources such as central laboratories will be reconciled to the clinical database.

All AEs will be coded using MedDRA. SAEs in the clinical database will be reconciled with the safety database.

10.1.6.4. Study Documentation and Storage

The Investigator will maintain a Signature List of appropriately qualified persons to whom he/she has delegated study duties. All persons authorized to obtain informed consent and make entries and/or corrections on eCRFs will be included on the Signature List.

Investigators will maintain a confidential screening log of all potential study candidates that includes limited information of the subjects, date and outcome of the screening process.

Investigators will be expected to maintain an Enrollment Log of all subjects enrolled in the study indicating their assigned study number.

Investigators will maintain a confidential SID code list. This confidential list of names of all subjects allocated to study numbers on enrolling in the study allows the Investigator to reveal the identity of any subject when necessary.

Source documents are original documents, data, and records from which the subject’s eCRF data are obtained. These include but are not limited to hospital records, clinical and office charts, laboratory and pharmacy records, diaries, microfiches, X-rays, and correspondence.

Electronic CRF entries may be considered source data if the eCRF is the site of the original recording (ie, there is no other written or electronic record of data). In this study, the study eCRF may be used as source documents.

Records of subjects, source documents, monitoring visit logs, data correction forms, eCRFs, inventory of study drug, regulatory documents (eg, protocol and amendments, IRB

correspondence and approvals, approved and signed ICFs, Investigator's Agreement, clinical supplies receipts, distribution and return records), and other Sponsor correspondence pertaining to the study must be kept in appropriate study files at the study site (site specific Trial Master File). Source documents include all recordings and observations or notations of clinical activities and all reports and records necessary for the evaluation and reconstruction of the clinical study. These records will be retained in a secure file for the period required by local laws or regulations or study site policy. Prior to transfer or destruction of these records, the Sponsor must be notified in writing and be given the opportunity to provide further instruction.

10.1.6.5. Record Keeping

The Investigators and study staff are responsible for maintaining a comprehensive and centralized filing system (site specific Trial Master File) of all study-related (essential) documentation, suitable for inspection at any time by representatives from the Sponsor and/or applicable regulatory authorities. Essential documents include:

- Subject files containing completed eCRFs, ICFs, and supporting source documentation (if kept).
- Study files containing the protocol with all amendments, IB, copies of relevant essential documents required prior to commencing a clinical study, and all correspondence to and from the independent IRB and the Sponsor.
- Records related to the study drug(s) including acknowledgment of receipt at study site, accountability records and final reconciliation and applicable correspondence.

In addition, all original source documents supporting entries in the eCRFs must be maintained and be readily available.

All essential documentation will be retained by the Investigator until at least 2 years after the last approval of a marketing application in an ICH region and until there are no pending or contemplated marketing applications in an ICH region or at least 2 years have lapsed since the formal discontinuation of clinical development of the investigational drug. These documents should be retained for a longer period, however, if required by the applicable laws or regulatory requirements or by an agreement with the Sponsor. It is the responsibility of the Sponsor to inform the Investigator/Institution as to when these documents no longer need to be retained.

Subjects' medical files should be retained in accordance with applicable legislation and in accordance with the maximum period of time permitted by the hospital, institution or private practice.

No study document should be destroyed without prior written agreement between the Sponsor and the Investigator. Should the Investigator wish to assign the study records to another party or move them to another location, he/she must notify the Sponsor in writing of the new responsible person and/or the new location.

10.1.7. Finances

[figure not shown]
Prior to starting the study, the Principal Investigator and/or Institution will sign a clinical study agreement with CRO. This agreement will include the financial information agreed upon by the parties.

10.1.8. Reimbursement, Indemnity, and Insurance

The Sponsor provides insurance for study subjects to make available compensation in case of study-related injury.

Reimbursement, indemnity and insurance shall be addressed in a separate agreement on terms agreed upon by the parties.

10.1.9. Publication and Public Disclosure Policy

10.1.10. Protocol Deviations

The Investigator should conduct the study in compliance with the protocol agreed to by the Sponsor and, if required, by the regulatory authority(ies), and which was given approval/favorable opinion by the IRBs.

A deviation to any protocol procedure or waiver to any stated criteria will not be allowed in this study except where necessary to eliminate immediate hazard(s) to the subject.

The Sponsor must be notified in writing of all intended or unintended deviations to the protocol (eg, inclusion/exclusion criteria, dosing, missed study visits) within 24 hours and in accordance with the clinical study agreement between the parties.

The Investigator, or person designated by the Investigator, should document and explain any deviation from the approved protocol.

If a subject was ineligible or received the incorrect dose or study treatment, and had at least one administration of study drug, data should be collected for safety purposes.

If applicable, the Investigator should notify the IRB of deviations from the protocol in accordance with local procedures.

10.1.11. Study and Site Closure

The Sponsor reserves the right to close the study site or terminate the study at any time for any reason at the sole discretion of the Sponsor. Study sites will be closed upon study completion. A study site is considered closed when all required documents and study supplies have been collected and a study-site closure visit has been performed.

The Investigator may initiate study-site closure at any time, provided there is reasonable cause and sufficient notice is given in advance of the intended termination.

Reasons for the early closure of a study site by the Sponsor or Investigator may include but are not limited to:

- Failure of the Investigator to comply with the protocol, the requirements of the IRB or local health authorities, the Sponsor's procedures, or GCP guidelines
- Inadequate recruitment of subjects by the Investigator
- Discontinuation of further study intervention development

10.1.12. Product Complaints

A product complaint is any dissatisfaction with a product that may be attributed to the identity, quality, durability, reliability, or safety of the product. Individuals who identify a potential product complaint situation should immediately report the event. Whenever possible, the associated product should be maintained in accordance with the label instructions pending further guidance from a quality representative from the Sponsor.

For product complaints, refer to the Pharmacy Manual for instructions and details.

10.2. Appendix 2: Central and/or Local Laboratory

The clinical laboratory tests listed in [Table 10.1](#) are to be performed in this study.

Table 10.1: Clinical Laboratory Tests

Test	Analytes	
Blood Chemistry	albumin albumin globulin (A/G) ratio alanine aminotransferase (ALT) alkaline phosphatase (ALP) aspartate aminotransferase (AST) bicarbonate/CO ₂ bilirubin (total) bilirubin (direct) blood urea nitrogen (BUN)/urea calcium (Ca) chloride (Cl) creatinine cholesterol (total)	creatine phosphokinase gamma-glutamyl transaminase (GGT) glucose ([non-fasting/fasting]) lactate dehydrogenase lipase lipoprotein, high density (HDL) lipoprotein, low density (LDH) magnesium (Mg) phosphorus potassium (K) protein (total) sodium (Na) triglycerides uric acid
Troponin	high sensitivity troponin-I troponin-T	

Test	Analytes	
Hematology	hemoglobin hematocrit platelet count red blood cell (RBC) count white blood cell (WBC) count mean corpuscular hemoglobin mean corpuscular hemoglobin concentration mean corpuscular volume	differential WBC count: basophils eosinophils lymphocytes monocytes neutrophils
Coagulation	prothrombin time (PT)/international normalized ratio (INR)	
Urinalysis (abbreviated)	bilirubin glucose ketone bodies occult blood pH protein	urobilinogen sediments: casts RBC WBC

10.3. Appendix 3: Reference Standards

10.3.1. Cockcroft-Gault Equation

The estimated CrCl (mL/min) will be calculated using the Cockcroft-Gault equation⁴ based on [actual/ideal] weight in kilograms (1 kilogram = 2.2 pounds):

Conventional – serum creatinine in mg/dL:

Male:

$$\text{CrCl (mL/min)} = \frac{[140 - \text{age (in y)}] \times \text{weight (in kg)}}{\text{serum creatinine (in mg/dL)} \times 72}$$

Female:

$$\text{CrCl (mL/min)} = \frac{[140 - \text{age (in y)}] \times \text{weight (in kg)}}{\text{serum creatinine (in mg/dL)} \times 72} \times 0.85$$

International System of Units (SI) – serum creatinine in $\mu\text{mol/L}$:

Male:

$$\text{CrCl (mL/min)} = \frac{[140 - \text{age (in y)}] \times \text{weight (in kg)}}{\text{serum creatinine (in } \mu\text{mol/L)} \times 72 \times 0.0113}$$

Female:

$$\frac{[140 - \text{age (in y)}] \times \text{weight (in kg)}}{\text{serum creatinine (in } \mu\text{mol/L)} \times 72 \times 0.0113}$$

10.3.2. CYP3A4 Inhibitors and Inducers

Table 10.2 lists the generic names of strong, moderate, and weak CYP3A4 inhibitors.

Table 10.2: CYP3A4 Inhibitors

Inhibitor Type	Generic Drug Name	Allowance
Strong	boceprevir cobicistat danoprevir and ritonavir elvitegravir and ritonavir grapefruit juice indinavir and ritonavir itraconazole ketoconazole, lopinavir, and ritonavir paritaprevir and ritonavir and (ombitasvir and/or dasabuvir) posaconazole ritonavir saquinavir and ritonavir telaprevir tipranavir and ritonavir telithromycin troleandomycin voriconazole	Use is prohibited
Moderate	aprepitant ciprofloxacin conivaptan crizotinib cyclosporine diltiazem dronedarone erythromycin fluconazole fluvoxamine imatinib tofisopam verapamil	Use is prohibited
Weak	chlorzoxazone cilostazol cimetidine clotrimazolefosaloprepitant istradefylline ivacaftor lomitapide ranitidine ranolazine ticagrelor	Use is prohibited

Source: <https://www.fda.gov/drugs/drug-interactions-labeling/drug-development-and-drug-interactions-table-substrates-inhibitors-and-inducers#table3-2>

Table 10.3 lists the generic names of strong, moderate, and weak CYP3A4 inducers.

Table 10.3: CYP3A4 Inducers

Inducer Type	Generic Drug Name	Allowance
Strong	apalutamide carbamazepine enzalutamide mitotane phenytoin rifampin St. John's wort	Use is prohibited
Moderate	bosentan efavirenz etravirine phenobarbital primidone	Use is prohibited
Weak	armodafinil modafinil rufinamide	Use is prohibited

Source: <https://www.fda.gov/drugs/drug-interactions-labeling/drug-development-and-drug-interactions-table-substrates-inhibitors-and-inducers#table3-3>

10.4. Appendix 4: General Information - Adverse Events

10.4.1. Definition of Adverse Event

An AE is any untoward medical occurrence in a subject administered a pharmaceutical product and that does not necessarily have to have a causal relationship with this treatment. An AE can therefore be any unfavorable and unintended sign (including an abnormal laboratory finding, for example), symptom, or disease temporally associated with the use of a medicinal product, whether or not considered related to the medicinal product.

It is the responsibility of Investigators, based on their knowledge and experience, to determine those circumstances or abnormal laboratory findings which should be considered AEs.

Events Meeting the AE Definition

- Any abnormal laboratory test results (hematology, clinical chemistry, or urinalysis) or other safety assessments (eg, ECG, radiological scans, vital signs measurements), including those that worsen from baseline, considered clinically relevant in the medical and scientific judgment of the Investigator (ie, not related to progression of underlying disease).
- Exacerbation of a chronic or intermittent pre-existing condition including either an increase in frequency and/or intensity of the condition.

- New conditions detected or diagnosed after study intervention administration even though it may have been present before the start of the study.
- Signs, symptoms, or the clinical sequelae of a suspected drug-drug interaction.
- Signs, symptoms, or the clinical sequelae of a suspected overdose of either study intervention or a concomitant medication.

Events NOT Meeting the AE Definition

- Any clinically relevant abnormal laboratory findings or other abnormal safety assessments which are associated with the underlying disease, unless judged by the Investigator to be more severe than expected for the subject's condition.
- The disease/disorder being studied or expected progression, signs, or symptoms of the disease/disorder being studied, unless more severe than expected for the subject's condition.
- Medical or surgical procedure (eg, endoscopy, appendectomy): the condition that leads to the procedure is the AE.
- Situations in which an untoward medical occurrence did not occur (social and/or convenience admission to a hospital).

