8.6.2.7.1. Hepatic Events

Hepatic events (both serious and non-serious) which meet the criteria below should be reported as AESI:

- **For healthy subjects:** an elevated (ALT and/or AST) $\geq 3 \times$ ULN and an elevated TBil $>2 \times$ ULN,
- **For hepatically impaired subjects:** Taking into consideration the NCI-ODWG criteria for moderate HI (which requires any elevation of ALT or AST and TBil $>1.5-3 \times$ ULN), worsening of baseline hepatobiliary parameters should be considered. Worsening of baseline values defined as an increase of 3 \times the baseline ALT and/or AST value AND increase of TBil from baseline, with increased TBil values being at least $>2 \times$ ULN.

These events must be reported with the Investigator’s assessment of seriousness, severity, causality, and a detailed narrative. These events should be reported within 24 hours of

Investigator's awareness of the event regardless of seriousness. A targeted questionnaire will be available as an eCRF to collect relevant additional information for these potential cases. Please refer to Section 10.7 for NCI-ODWG criteria table.

If the subject discontinues study drug due to liver enzyme abnormalities, the subject will have additional clinical and laboratory evaluations as described in Section 10.2 in order to determine the nature and severity of the potential liver injury.

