8.6.3. Clinical Laboratory Evaluations

Clinical laboratory evaluations will be performed as detailed in the SoE in Section 1.3.

The clinical laboratory tests will include hematology, coagulation, blood chemistry, and urinalysis. Refer to Section 10.2 for the complete list of laboratory parameters.

Allowable time windows for safety laboratory collections are provided in Section 10.7.

Abnormal laboratory values occurring during the clinical study will be followed until repeat test results return to normal (or baseline), stabilize, or are no longer clinically relevant. New or worsened clinically relevant laboratory abnormalities should be recorded as AEs.

Urine drugs of abuse, cotinine, alcohol screen will be tested during the Screening and Check-in. A breath test is also acceptable for alcohol screening

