9.5.1. Safety Analyses

9.5.1.1. Adverse Events

TEAEs are defined as new AEs that occur after the first dose of study drug or as AEs that were present prior to first dose of study drug but which worsened in severity after the start of study drug. AEs collected 30 days after the last dose of study drug will not be considered TEAEs unless they are treatment-related. AEs will be coded using the Medical Dictionary for Regulatory Activities (MedDRA). An AE will be assigned to the study day in which it started,

even if it resolved on a subsequent day. The incidence of TEAEs will be summarized by treatment group. The number and percentage of subjects reporting TEAEs will be calculated overall, by system organ class, by preferred term, and by treatment group.

TEAEs will be further summarized by CTCAE grade and relationship to study drug. Similarly, the number and percentage of subjects reporting treatment-emergent SAEs and related treatment-emergent SAEs will be tabulated, treatment-emergent AESIs, and TEAEs leading to discontinuation of study drug.

A by-subject AE (including treatment-emergent) data listing including but not limited to verbatim term, preferred term, system organ class, CTCAE grade, and relationship to study drug will be provided. Deaths, SAEs, AESIs, and AEs associated with study drug discontinuation, will be listed.

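### The AE definition in Section 10.4.1 can leave postdose hepatic worsening unrecorded in the HI cohort only, and it conflicts with Sections 8.6.3 and 8.6.4

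*Combined protocol and SAP*

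**What the plan says.** Section 10.4.1 (Appendix 4) removes two classes of finding from the AE definition. The first is "Any clinically relevant abnormal laboratory findings or other abnormal safety assessments which are associated with the underlying disease", with the proviso "unless judged by the Investigator to be more severe than expected for the subject's condition". The second is "The disease/disorder being studied or expected progression, signs, or symptoms of the disease/disorder being studied", with a similar proviso. The positive laboratory criterion in the same section is also limited: an abnormal or worsening result counts if "considered clinically relevant in the medical and scientific judgment of the Investigator (ie, not related to progression of underlying disease").

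Other text points the other way. Among events that do meet the definition, Section 10.4.1 lists "Exacerbation of a chronic or intermittent pre-existing condition including either an increase in frequency and/or intensity of the condition". Section 8.6.3 states: "New or worsened clinically relevant laboratory abnormalities should be recorded as AEs". Section 8.6.4 has a parallel rule for physical examination findings. Neither 8.6.3 nor 8.6.4 has an exception for underlying disease.

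Hepatic events are one of the drug's two AESIs. Section 8.6.2.7 defines them for all subjects. Section 8.6.2.7.1 and Appendix 8 then give HI subjects a baseline-relative rule, on the ground that "worsening of baseline hepatobiliary parameters should be considered". TEAEs form part of a secondary endpoint (Section 3.2) and are tabulated by group (Section 9.5.1.1).

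**The concern.** In this trial the underlying disease is liver disease, and it is also what separates the two cohorts. An AE exclusion tied to that disease cannot act equally on both. A postdose worsening of liver tests or hepatic signs in an HI subject can be set aside as the expected course, while the same change in a control has no disease to be set against and is recorded.

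What is at stake is the descriptive comparison of hepatic TEAEs between groups, in the population the study is meant to inform and for an organ with a known AESI. The judgement is made by an investigator who knows the cohort (Section 6.3.2), against a standard the protocol does not define. It is also made before any record exists, so an event set aside this way gets no AE entry and no causality assessment.

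**Working it through.** The plan gives no figure to reproduce. The check sets the rules side by side, applies them to one case, and then does the arithmetic on size.

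**1. Which cohort is exposed.** Exclusion 25 (Section 5.2) bars controls whose liver tests are above ULN. HI subjects must have chronic liver disease and TBil >1.5 to 3 × ULN (Section 5.1, criterion 7). The exclusions in 10.4.1, applied to liver disease, can therefore operate only in HI subjects.

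**2. Test case (assumed values).** An HI subject's TBil rises from 2 to 4 × ULN, with ALT and AST stable and ALT not above 3 × ULN.

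- Section 8.6.2.7 needs ALT >3 × ULN and TBil >2 × ULN. The TBil limb is met (4 > 2) and the ALT limb is not. Not an AESI.
- Section 8.6.2.7.1 and Appendix 8 need ALT and/or AST at 3 × baseline, plus a TBil rise to >2 × ULN. The ALT and AST ratio is 1, below 3. Not an AESI.
- Section 8.6.3: an AE if clinically relevant.
- Section 10.4.1, exacerbation bullet: an AE if the rise is read as increased intensity of a pre-existing condition.
- Section 10.4.1, laboratory criterion: not an AE if ascribed to progression of the liver disease.
- Section 10.4.1, exclusions: not an AE unless judged more severe than expected.

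The AESI rules are silent, and AE status depends on whether 8.6.3 or 10.4.1 governs. Section 8.6.3 does not clearly prevail: a site that carries the gloss on clinical relevance from 10.4.1 into 8.6.3 would not record the event. A control whose TBil reached the same level would be recorded under 8.6.3 if the finding were clinically relevant.

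**3. How far the AESI rule acts as a backstop.** For controls the ALT/AST limb is 3 × ULN. For HI subjects it is 3 × baseline. With an assumed baseline ALT of 1, 2 or 3 × ULN (Appendix 8 allows any value), the limit is 3 × 1 = 3, 3 × 2 = 6 or 3 × 3 = 9 × ULN. A rise in TBil alone never meets this rule.

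**4. Size.** Section 9.5.1.1 counts subjects, overall and by system organ class and preferred term. With 8 HI subjects (Section 9.2), one subject is 1/8 = 12.5 percentage points. A lost event changes the overall row by that amount only if the subject has no other TEAE, and a class or term row only if the subject has no other TEAE in that row.

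**The case against.** The strongest reply is that the exclusion is conditional and surrounded by safeguards. A finding worse than expected remains an AE. Read with that proviso, the exacerbation bullet need not contradict the exclusion. Exclusion 27 removes subjects whose liver function is unstable or quickly worsening, so a marked change by Day 22 would be hard to call expected. Section 8.6.2.1 requires all laboratory results to be appraised, and isolated abnormalities to be reported if they are symptomatic, need corrective treatment or are an AE in the investigator's judgement. Section 9.5.1.2 tabulates change from baseline and CTCAE shifts by group whether or not an AE is recorded. Safety is descriptive and no hypothesis is tested (Section 9.1).

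Most of this stands and limits the point. It does not remove the conflict between 10.4.1 and Sections 8.6.3 and 8.6.4. The laboratory tables carry no causality assessment and do not cover signs such as ascites or encephalopathy; physical findings are only listed (Section 9.5.1.5).

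Four stronger readings are tempting, and the documents do not support them:

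- *The TEAE definition contradicts the exclusion.* Section 9.5.1.1 refers to "AEs that were present prior to first dose of study drug but which worsened in severity after the start of study drug". It acts on events already classed as AEs and does not decide what an AE is. Section 8.3 sends predose findings to medical history.
- *Worsening below the AESI limits would go ungraded.* Section 9.5.1.2 grades abnormal laboratory results by CTCAE where applicable, independently of AE status.
- *An ALT rise from 1.5 to 3.75 × ULN with TBil rising from 1.8 to 2.6 × ULN escapes both AE and AESI status.* It misses the HI-specific rule (3.75/1.5 = 2.5, below 3) but meets the general definition in 8.6.2.7 (3.75 > 3 and 2.6 > 2). Its AESI status is therefore arguable, although 8.6.2.4 points to 8.6.2.7.1 for reporting.
- *Every lost event costs 12.5 points.* This is true only under the condition in step 4 of the working.

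**Conclusion.** The point holds as a conflict between stated rules with a one-sided effect. Sections 8.6.3 and 8.6.4 record clinically relevant worsening in everyone. Section 10.4.1 lets it be left out where it is ascribed to underlying disease, and for liver disease that can happen only in HI subjects. Any resulting bias in hepatic TEAE incidence is towards fewer events in the HI cohort.

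Its size cannot be estimated from the documents, because it depends on how often investigators would call a worsening expected. Exclusion 27 makes that less likely, and the laboratory tables would still show the numerical change. What would be missing is the AE record, its causality assessment, and any tabulation of worsening hepatic signs. The conclusion assumes that the treatment groups in Section 9.5.1.1 are the two hepatic function cohorts, since all subjects receive the same treatment. The test case uses assumed values.

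The change should be made: it corrects a rule that ascertains hepatic AEs differently by cohort, at little cost.

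**What to change.** In Section 10.4.1, state that the two underlying-disease exclusions, and the gloss that limits clinically relevant findings to those unrelated to disease progression, do not apply to hepatobiliary laboratory findings or hepatic signs that worsen from the last predose value. Record clinically relevant postdose worsening as an AE in both cohorts, in line with 8.6.3 and 8.6.4. Where the investigator believes the liver disease explains the event, enter that in the causality field; Section 10.4.5 already allows the disease under study as a ground for a not-related assessment.

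In the same amendment, reconcile the general hepatic AESI definition in 8.6.2.7 with the cohort-specific rules in 8.6.2.7.1 and Appendix 8. Reconcile also the HI transaminase wording, which is an increase of 3 × the baseline value in 8.6.2.7.1 but values at or above 3 × baseline in Appendix 8.

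The cost is a wording change in the protocol and in the eCRF completion instructions, plus a few more AE records in HI subjects, most of them likely to be assessed as unrelated.
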